6.10 DRUG SUPPLY AND STORAGE

Study drug must be received by the designated personnel at the study site, handled and stored safely and properly, and kept in a secured location to which only designated personnel have access. Upon receipt, the study drug should be stored according to the instructions specified on the drug labels and in the Investigators Brochure. Medication labels will comply with the legal requirements of each country and be printed in the local language.

6.11 STUDY DRUG COMPLIANCE AND ACCOUNTABILITY

6.11.1 Compliance

Compliance will be assessed by the investigator and/or study personnel at each patient visit and information provided by the patient via patient drug diary. Records of the study medication used, dosages administered, and intervals between visits and completion of the study will be captured in the Drug Accountability Form.

6.11.2 Accountability

The investigator or designee must maintain an accurate record of the shipment and dispensing of study treatment in a drug accountability log at the study close-out visit, and as appropriate during the course of the study.

6.12 DRUG ELUTING BEAD-CHEMOEMBOLIZATION

Chemoembolization is considered standard of care for locally advanced, non-metastatic HCC.

6.12.1 DC Bead description

a) DC bead comprise a range of hydrogel microspheres that are biocompatible, hydrophilic, non resorbable, precisely calibrated and capable of loading doxorubicin. DC bead is produced from polyvinyl alcohol and are available in the following size ranges:

Nominal bead size	Label color	Upon loading with doxorubicin, DC bead undergo a slight decrease in size, up to 20% when loading at 25 mg/ml
100-300 um	Yellow	
300-500 um	Blue	
500-700 um	Red	
700-900 um	Green	

b) How supplied:

- 10 ml glass vial
- Each vial contains approximately 2 ml of DC bead in non-pyrogenic, sterile, physiological buffered saline. Total volume of saline and DC bead is approximately 8 ml.
- The vial is stopper sealed by an aluminum cap equipped with a color-coded lid
- Each vial is intended for single patient use only. Do not resterilize. Discard any unused material

C) Contraindications-DC bead

- Patients intolerant to vascular occlusion procedures
- Vascular anatomy that precludes catheter placement or emboli injection
- Presence or likely onset of vasospasm

- Presence of likely onset of hemorrhage
- Presence of severe atheromatous disease
- Presence of feeding arteries smaller than distal branches from which they emerge
- Presence of patent extra-to-intracranial anastomoses or shunts
- Presence of collateral vessel pathways potentially endangering normal territories during embolization
- Presence of end arteries leading directly to cranial nerves
- Presence of arteries supplying the lesion not large enough to accept DC bead
- Vascular resistance peripheral to the feeding arteries precluding passage of DC bead into the lesion
- Do not use DC bead for embolization of large diameter arteriovenous shunts

6.12.2 DRUG LOADING INSTRUCTIONS

DC bead is suitable for loading doxorubicin-HCL only. Liposomal formulations of doxorubicin are not suitable for loading into DC bead.

To obtain final loading of 50 mg per 2 ml vial of DC bead;

- I. Reconstitute a vial containing 50 mg of doxorubicin with 2 ml of sterile water for injection. Mix well to obtain a clear red solution (25 mg/ml).
- II. Remove as much saline as possible from vial of DC bead using a syringe with a small gauge needle.
- III. Using a syringe and needle add the 2 ml of reconstituted doxorubicin solution directly to the vial of DC bead.
- IV. Agitate the DC bead/doxorubicin solution occasionally to encourage mixing until the DC bead is red. Although the solution retains a red color, doxorubicin will be loaded.
- V. Loading will take a minimum of 20 minutes for the smallest size DC bead and up to 120 minutes for the largest DC bead.
- VI. Prior to use, transfer the DC bead loaded with doxorubicin to a syringe and add 1 to 4 times the volume of the non-ionic contrast media, Omnipaque 350. Invert the syringe gently to obtain an even suspension of DC bead. A dose of up to 37.5 doxorubicin per ml DC bead can be loaded.
- VII. The maximum recommended total dose of doxorubicin per procedure is 150 mg.

6.12.3 PATIENT PRE-PROCEDURAL PREPARATION

- a) IV normal saline
- b) Pre-medications
 - a. Versed and Fentanyl titrated for moderate sedation

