6.9 CONCOMITANT MEDICATIONS

Permitted Concomitant Therapy

Medications required to treat AEs, manage cancer symptoms, concurrent diseases and supportive care agents, such as pain medications, anti-emetics and anti-diarrheal are allowed.

The patient must be told to notify the investigational site about any new medications s/he takes after the start of the study treatment. All medications (other than study drugs) and significant non-drug therapies (including vitamins, physical therapy and blood transfusions) administered within 30 days of study entry and during the study must be listed on the Concomitant medications/Significant non-drug therapies section of the patient record.

Bisphosphonates and Denosumab

Bisphosphonates and denosumab are permitted for the treatment of osteoporosis and prevention of skeletal related events for patients with bone metastases. Chronic concomitant bisphosphonate/denosumab therapy for the prevention of bone metastasis is not permitted.

Hematopoietic Growth Factors

Hematopoietic growth factors may be used according to ASCO guidelines.

Palliative Radiotherapy

Palliative radiation is permitted if done solely for bone pain relief. It should not be delivered to a target lesion and it should not encompass more than 25% of irradiated bone marrow. Refer to the LEE011 (LEE011) Investigator's Brochure, Appendix table 1, and Appendix table 2 for information on possible interactions with other drugs.

Permitted Concomitant Therapy Requiring Caution

Medications to be used with caution during LEE011 in this study are listed below (**see Table 2**). This list is not comprehensive and is only meant to be used as a guide. Concurrent use of CYP1A2 substrates is not expected to lead to clinically important drug-drug interactions, therefore their use is not regulated. These medications should be excluded from patient use if possible. If they must be given, then use with caution and consider a LEE011 interruption if the concomitant medication is only needed for a short time (**See Appendix Table 1**):

- Moderate inhibitors or inducers of CYP3A4/5;
- Sensitive substrates of CYP3A4/5 that do not have narrow therapeutic index;
- Strong inhibitors of BSEP;
- Sensitive substrates of the renal transporters, MATE1 and OCT2;
- Sensitive substrates of BCRP;
- Medications that carry a possible risk for QT prolongation

Prohibited Concomitant Therapy

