The following medications are prohibited during study treatment in the study (**see Appendix Table 2**). This list is not comprehensive and is only meant to be used as a guide:

- Strong inhibitors or inducers of CYP3A4/5;
- Substrates of CYP3A4/5 with a narrow therapeutic index;
- Medications that carry a known risk for QT prolongation;
- Herbal medications/preparations, herbal dietary supplements;
- Other investigational and antineoplastic therapies not part of the study;
- Herbal medications include, but are not limited to: St. John's Wort, Kava, ephedra (ma huang), ginkgo biloba, dehydroepiandrosterone (DHEA), yohimbe, saw palmetto, black cohosh and ginseng. Patients should stop using all herbal medications and dietary supplements at least 7 days prior to first dose of study treatment.

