19.0 APPENDICES

In general, the use of any concomitant medication deemed necessary for the care of the patient is permitted in this study, except as specifically prohibited below. Combination administration of study drugs could result in drug-drug interactions (DDI) that could potentially lead to reduced activity or enhanced toxicity of the concomitant medication and/or LEE011.

The following lists are not comprehensive and are only meant to be used as a guide. The lists are based on the Oncology Clinical Pharmacology Drug-Drug Interaction Database (release date: 29 Oct 2012), which was compiled from the Indiana University School of Medicine's P450 Drug Interaction Table (<http://medicine.iupui.edu/clinpharm/ddis/main-table/>) and supplemented with the FDA Draft Guidance for Industry, Drug Interaction Studies – Study Design, Data Analysis, and Implications for Dosing and Labeling (February 2012) (<http://www.fda.gov/downloads/drugs/guidancecomplianceregulatoryinformation/guidances/ucm292362.pdf>), and the University of Washington's Drug Interaction Database (<http://www.druginteractioninfo.org/>). For current lists of medications that may cause QT prolongation and/or torsades de pointes (TdP), refer to the CredibleMeds® website (<https://crediblemeds.org/>). Please contact the medical monitor with any questions.

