Appendix Table 2: List of prohibited medications during study drug treatment

Category	Drug Name
Strong CYP3A4/5 inhibitors	Boceprevir, clarithromycin, cobicistat, conivaptan, elvitegravir, indinavir, itraconazole, ketoconazole, lopinavir, mibefradil, nefazodone, nelfinavir, posaconazole, ritonavir, saquinavir, telaprevir, telithromycin, tipranavir, troleandomycin, voriconazole
Strong CYP3A4/5 inducers	Avasimibe ^{2,3} , carbamazepine, mitotane, phenobarbital, phenytoin, rifabutin, rifampin (rifampicin) ³ , St. John's wort (hypericum perforatum) ³
CYP3A4/5 substrates with NTI ¹	Alfentanil, astemizole, cisapride, cyclosporine, diergotamine (dihydroergotamine), ergotamine, fentanyl, pimozone, quinidine, sirolimus, tacrolimus, terfenadine
Medications with a known risk for QT prolongation ⁴	Amiodarone, arsenic trioxide, astemizole, azithromycin, bepridil, chloroquine, chlorpromazine, cisapride, citalopram, clarithromycin, disopyramide, dofetilide, domperidone, droperidol, erythromycin, flecainide, halofantrine, haloperidol, ibutilide, levomethadyl, mesoridazine, methadone, moxifloxacin, pentamidine, pimozone, probucol, procainamide, quinidine, sotalol, sparfloxacin, terfenadine, thioridazine, vavdetanib
Herbal preparations/medications	Herbal preparations/medications are prohibited throughout the study. These herbal medications include, but are not limited to: St. John's wort, Kava, ephedra (ma huang), ginkgo biloba, dehydroepiandrosterone (DHEA), yohimbe, saw palmetto, and ginseng. Patients should stop using these herbal medications 7 days prior to first dose of study drug.
Other investigational and antineoplastic therapies	Other investigational therapies must not be used while the patient is on the study. Anticancer therapy (chemotherapy, biologic or radiation therapy, and surgery) other than the study treatments must not be given to patients while the patient is on the study medication. If such agents are required for a patient then the patient must be discontinued study drug.

¹ NTI = narrow therapeutic index drugs whose exposure-response indicates that increases in their exposure levels by the concomitant use of potent inhibitors may lead to serious safety concerns (e.g., Torsades de Pointes).
 
² Herbal product
 
³ P-gp inducer
 
⁴ Source: www.crediblemeds.org
	

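### Fentanyl is named as chemoembolization pre-medication but is on the list of drugs prohibited during LEE011 treatment, and nothing reconciles the two for repeat procedures

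*Combined protocol and SAP*

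**What the plan says.** Section 6.12.3 lists the pre-medication for chemoembolization (TACE) as "Versed and Fentanyl titrated for moderate sedation". It does not separate the first TACE from later ones.

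Section 6.9, under prohibited therapy, includes "Substrates of CYP3A4/5 with a narrow therapeutic index" and points to Appendix Table 2, headed "List of prohibited medications during study drug treatment". That table's narrow-therapeutic-index row contains "ergotamine, fentanyl, pimozone, quinidine, sirolimus, tacrolimus, terfenadine".

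Repeat TACE is part of the design. Section 6.12.7 allows up to four procedures within 6 months of the first, at least 4 weeks apart, and Section 7.3.1 gives a 28-day interval. Section 6.12.7 sets laboratory and toxicity limits, spacing and number. It contains no sedation rule and no LEE011 hold.

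**The concern.** The first TACE comes before LEE011, so the two rules need not meet there. At a repeat TACE the patient may be taking LEE011. Interventional radiology staff working from Section 6.12 would then expect to give fentanyl, while research staff working from Section 6.9 and its appendix would expect it to be barred.

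The stake is patient safety, in a limited sense: a routine procedural step has no single instruction and would need a ruling each time. Section 17.0 requires conduct exactly as the protocol describes, and Section 17.2 requires prior approval for planned deviations. Case-by-case rulings are a poor substitute for consistent text.

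Midazolam is not part of this point, because Appendix Table 1 places it on the caution list only.

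**Working it through.** **1. Does any passage resolve the conflict?** There is no trial figure to reproduce, so the candidate passages are set side by side.

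| Candidate | What it covers | Resolves it? |
|---|---|---|
| Section 6.9, general allowance for pain and supportive medication | Names neither fentanyl nor TACE sedation. Section 19.0 says "the use of any concomitant medication deemed necessary for the care of the patient is permitted in this study, except as specifically prohibited below" | No: the general permission yields to the list |
| Section 6.9, interruption option: "If they must be given, then use with caution and consider a LEE011 interruption" | The caution list (Appendix Table 1), which does not include fentanyl | No |
| Table 7.1 footnote 7 and Section 11.0, LEE011 hold of 24-48 hours | Biopsy | No |
| LEE011 Administration with Chemoembolization (after 6.12.6), 7-day rule | Starting LEE011 after TACE | No: it sets no hold before TACE |
| Table 7.1 footnote 13 | Use of the post-TACE visit as a cycle's Day 1 | No hold is written, though a gap may be implied |
| Section 6.9: "This list is not comprehensive and is only meant to be used as a guide"; Section 19.0: "Please contact the medical monitor with any questions" | Status of the lists; a route for questions | Softens the conflict but does not exempt a named drug |

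**2. Can a repeat TACE fall on a LEE011 dosing day?**

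Inputs:
- Dosing on days 1-21 of a 28-day cycle (Section 6.3).
- LEE011 starts no earlier than 7 days after TACE. The post-TACE clinic visit, where the decision to start is made, is at 7-10 days (Section 6.12.6).
- Repeat TACE at 28 days or later (Sections 6.12.7 and 7.3.1).

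Assumption: cycles run without interruption or re-start around the second TACE.

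Formula: cycle day of second TACE = ((T - s) mod 28) + 1. Here T is the day of the second TACE and s the day of the first LEE011 dose, both counted from the first TACE. Results of 1 to 21 are dosing days.

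| T | s = 7 | s = 8 | s = 9 | s = 10 | Starts on a dosing day |
|---|---|---|---|---|---|
| 28 | 22 | 21 | 20 | 19 | 3 of 4 |
| 29 | 23 | 22 | 21 | 20 | 2 of 4 |
| 30 | 24 | 23 | 22 | 21 | 1 of 4 |
| 31 | 25 | 24 | 23 | 22 | 0 of 4 |
| 34 | 28 | 27 | 26 | 25 | 0 of 4 |
| 35 | 1 | 28 | 27 | 26 | 1 of 4 |
| 36 | 2 | 1 | 28 | 27 | 2 of 4 |
| 37 | 3 | 2 | 1 | 28 | 3 of 4 |
| 38 | 4 | 3 | 2 | 1 | 4 of 4 |
| 55 | 21 | 20 | 19 | 18 | 4 of 4 |

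Days 31-34 are all 0 of 4, and days 38-55 are all 4 of 4.

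The protocol allows up to 28 days for the LEE011 start criteria to be met. Over all starts from day 7 to day 28, a TACE on day 28 falls on cycle day 28 - s + 1. That is day 22 for s = 7 and days 21 down to 1 for s = 8 to 28, so 21 of 22 start days give a dosing day. These are counts of start days, not expected frequencies.

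**3. Sensitivity to the assumption.** Suppose no new cycle begins until after the repeat TACE. Cycle 1 dosing then ends on day s + 20, which is day 27, 28, 29 or 30 for s = 7 to 10. The overlap is unchanged on days 28-30 (3, 2 and 1 of 4) and is zero from day 31.

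**The case against.** The strongest contrary reading is that the lists are not aimed at procedural sedation. Section 6.9 prohibits a class, and only the appendix names fentanyl. Both places call the lists a guide, and the medical monitor is available for questions. Section 6.2 makes TACE part of study treatment, so a reader could treat its named sedation as part of the procedure and not as concomitant medication. Section 6.9 also applies during study treatment, which on that definition would bar fentanyl even at the first TACE. Appendix Table 2 refers to study drug treatment. This difference in period is real. It is a further inconsistency, and it does not create an exemption.

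The timing table is also open to challenge. It depends on uninterrupted cycles, and footnote 13 together with the post-TACE start criteria may imply a re-start. Table 7.1 marks TACE and LEE011 in the same Day 1 columns, but it does so even for Cycle 1, where TACE must come at least 7 days earlier, so the marks cannot all be literal. Neither the list nor Section 6.9 says whether the prohibition lapses in the rest week. These points stand. The table therefore shows that overlap is possible under ordinary timing, and does not estimate how often it occurs.

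Finally, the risk is not quantified. Section 1.7.1 says LEE011 may inhibit CYP3A4 substrates if concentrations are high enough, and the safety footnote to Appendix Table 2 concerns potent inhibitors. Sedation is titrated and patients are observed overnight. This limits the weight of the point but does not remove the contradiction.

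**Conclusion.** The concern holds. For a repeat TACE during LEE011 treatment, Section 6.12.3 names a drug that Section 6.9 and Appendix Table 2 together prohibit, and no exemption or hold is written.

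At the 28-day minimum interval, three of the four start days from 7 to 10 put the procedure on a dosing day, with or without a cycle re-start. For later dates the answer runs from none to all four, depending on the date and on whether cycles continue uninterrupted. Exposure is limited to repeats that are indicated, at most three per patient in the first 6 months (4 - 1 = 3). The number of affected procedures and the size of any interaction cannot be derived from the documents.

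The conclusion makes no claim about the first TACE or about a TACE in a rest week. It takes no view on which instruction is clinically right.

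**What to change.** Reconcile Sections 6.12.3 and 6.12.7 with Section 6.9 and Appendix Table 2, so that the protocol gives one instruction on procedural sedation at any TACE performed after LEE011 has started. The same amendment should align the period the prohibition covers, which Section 6.9 and Appendix Table 2 describe differently. The content of the instruction is for the sponsor and the investigator to decide, with clinical pharmacology and interventional radiology input.

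The cost is a wording amendment with IRB approval under Section 17.3. There is no effect on sample size, endpoints or analysis.

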6.12.4 CHEMOEMBOLIZATION PROCEDURAL PREPARATION

- a) The patient is prepped and draped in a sterile fashion.
- b) Carefully evaluate the vascular network associated with the lesion with high resolution imaging prior to beginning the embolization procedure.

- c) DC beads are available in a range of sizes, but only 100 to 500 um particles should be utilized. Care should also be taken to choose the appropriate size of DC bead that bases matches the vascular target or vessel size.
- d) Choose a delivery catheter based on the size of the target vessel. DC bead can tolerate temporary compression of 20% to 30% in order to facilitate passage through the delivery catheter.
- e) Introduce the delivery catheter into the target vessel according to standard techniques. Position the catheter tip as close as possible to the treatment site to avoid inadvertent occlusion of normal vessels.
- f) DC are not radio-opaque. It is recommended to monitor the embolization under fluoroscopic visualization by adding the desired amount of contrast medium to the suspension fluid.
 - a. Take care to ensure proper suspension of the DC bead in the contrast medium to enhance distribution during injection.
 - b. Draw the DC bead into a syringe needle of a size greater than or equal to 19 gauge.
 - c. At a rate no faster than 1ml/minute, slowly inject DC bead into the delivery catheter under fluoroscopic visualization while observing the contrast flow rate. Exercise conservative judgment in determining the embolization endpoint.
- g) Upon completion of the treatment, remove the catheter while maintaining gentle suction so as not to dislodge the DC bead still within the catheter lumen.
- h) Discard any unused DC bead loaded with doxorubicin.

6.12.5 **POST-CHEMOEMBOLIZATION PROCEDURE ORDERS AND CARE**

- a) Admit patients overnight for observation.
- b) Hydration with IV normal saline
- c) Patient controlled analgesia for pain control.

6.12.6 **POST-PROCEDURE CARE**

- a) Post-arteriography bedrest with monitoring of vital signs and pulses.
- b) Patient can be discharged as soon as they demonstrate adequate oral intake or liquids, no longer require parenteral narcotics or antiemetics.
- c) Fevers <103 degrees F are normal during the first week following treatment and do not require cultures.
- d) Following institutional guidelines, patients will be seen in the HCC multidisciplinary clinic 7-10 days following chemoembolization and will have the following evaluations completed:
 - Physical examination
 - Comprehensive metabolic panel
 - Complete blood count without differential
 - Prothrombin time/INR

At this time the decision will be made to initiate LEE011 treatment.

LEE011 ADMINISTRATION WITH CHEMOEMBOLIZATION

Subjects are to be evaluated from toxicity with:

- Physical Examination (PE)
- Comprehensive Metabolic Panel (CMP)
- CBC
- ECG's

LEE011 will be initiated at the earliest of 7 days following embolization chemoembolization provided the following criteria are met:

- Serum bilirubin elevation $< 2.0 \times \text{ULN}$. If serum bilirubin $\geq 2.0 \times \text{ULN}$ then subjects will be assessed weekly and LEE011 will be initiated once bilirubin $< 2.0 \times \text{ULN}$.
- Resolution of Grade < 3 non-hematologic toxicity (other than bilirubin criteria above). If non-hematologic toxicity \geq Grade 3 then subjects will be assessed weekly and LEE011 will be initiated once $<$ Grade 2;
- Hematological toxicity of \leq Grade 2. If hematologic toxicity \geq Grade 3 then subjects will be assessed weekly and LEE011 will be initiated once \leq Grade 2.

If baseline AST, ALT and alkaline phosphate are elevated post chemoembolization decrease to baseline grade is necessary to continue/initiate LEE011;

- ECOG performance status ≤ 2 ;
- Serum AST, ALT, and/or Alkaline Phosphate $< 5 \times \text{ULN}$.

If criteria is not met, subjects will be reevaluated in 5-7 day intervals. If study subjects are unable to meet the above LEE011 starting criteria following initial chemoembolization treatment within 28 days after treatment, they will be removed from the study.

